9.4 Study Timelines

Subjects agree to participate for one year.

We propose a 5-year (60 month) timeline: formative evaluation, hiring and training, study setup (months 1-6); recruitment (months 7-42); trial implementation (months 7-55); data collection, cost tracking (months 7-55); stakeholder interviews, dissemination of efforts, analyses, presentations, and manuscripts (months 56-60).

9.5 Study Endpoints

The primary outcome is the BF continuation rate at 6-month postpartum. This is determined by observed breastfeeding which includes: audible swallowing, regular suck/swallow/breath patters, visible milk in the infant's mouth after the infant is not latched anymore. Or, in the case of pumping moms, pumped milk and successful feeding to the infant. We hypothesize that the isolated effect of monthly incentives contingent on BF in SC+BFI will increase BF rates by 25% at 6-month compared to SC.

The exploratory outcome is the BF continuation rate at 12-month postpartum. We will hypothesize that SC+BFI will increase the BF rate at 12-month, compared to SC.

10.0 Study Procedures Involved:

- 10.1 We will use a randomized, two-group design (Standard Care+Breastfeeding Support vs. Standard Care+Breastfeeding Incentives).
- 10.2 We will use a permuted block random assignment (with block size = 6), assigning participants to one of 2 groups: *Standard Care* or *Standard Care + BFI*. This will allow us to keep group sizes approximately equivalent during the study maintaining an approximately equal size for the 2 groups. We will use propensity score matching to randomize the participants based on study site, as well as Black race and Puerto Rican ethnicity to maximize internal validity.

Allocation to study groups in randomization will be administered by [name] (Co-I) who will not have access to collected data until the end of the study. [name] will generate computer-

generated random numbers and keeps the original sequence in a password-protected electronic file that no other research staff can access. [name] will program the list of random numbers into an electronic file on RedCap which will automatically assign each participant to either condition. Other research staff can only view the result of randomization so that the allocation process remains concealed.

Differences between the study arms are that Standard Care receives compensations at the end of 6 month based on the number of completed home visitations (\$40/home visit) and Standard Care + BFI receives compensations at every home visit appointment if they are breastfeeding. The compensation for Standard Care + BFI is in an escalating schedule in which the first home visitation receives \$20 increasing by \$10 at every month up to \$70 if they demonstrate breastfeeding every month. Participants in Standard Care + BFI also receive \$50 per selection of full breastfeeding food package at WIC, potentially at baseline, 3, and 6 months postpartum.

- 10.3** Standard Care BF Support (WIC support + home-based individual support; Standard Care[SC]). Participants in SC will receive standard BF services from the WIC program, receive education on family nutrition, monitor their monthly nutritional habit, and be asked to participate in periodic assessments (1-, 3-, 6-, 9-, and 12-month postpartum). Combined institutional and home-based individual BF support by WIC and home-visiting lactation counselors has been already available in the community for Hispanic mothers as the standard of care model. Each periodic assessment will take approximately 30 minutes to complete.

WIC support component: Standard services from WIC will include on-site lactation consultation, bilingual peer counseling, peer support meetings, free breast pump, and enhanced food package for BF mothers. On-site lactation consultation, bilingual peer counseling, and peer support meetings occur once a week in each WIC office. Free breast pumps are given to WIC participants who have not had the benefit by the time they enroll into WIC. Enhanced food packages for BF mothers are distributed to WIC participants every three months.

Home-based support and problem-solving component: Blinded RA will also provide individual support and problem-solving in addition to WIC services. At each monthly home visit, blinded RA will ask participants to demonstrate BF, praise participants' efforts to continue BF, problem-solve issues around BF, provide local BF resources, and identify any issues with BF and other medical and psychosocial needs. Signs to verify ongoing BF include audible swallowing of breastmilk, regular suck/swallow/breathing patterns, visible milk in an infant's mouth, and (in case of pumping moms) pumped milk and successful feeding of an infant. When a participant has trouble with BF, she will be referred to a certified lactation consultant (CLC). Should a participant report any adverse maternal and infant outcome during the study period, blinded RA will document the event, report to the PI and IRBs, and make referrals as needed. Participants in SC will be asked to monitor their nutritional habit each month and to complete 24-hour recalls for each month. Research staff will mark a tally on a checklist at each monthly visit, and completion of nutritional monitoring will lead to a lump sum compensation for a total potential earning of \$240 with \$40 per completed monthly nutritional monitoring. Participants will also receive diapers and wipes at every home visit. This is comparable to the SC+BFI group to control for the incentive amount. However, in SC, this payment is tied to monitoring the nutritional habit and paid in a lump sum— not to observed BF at each month as in the SC+BFI group.

If a participant misses an appointment, this will be counted as incompliance with monthly nutritional monitoring. The participant will be given an opportunity to make up for the missed appointment within one-week timeframe from a due date. Blinded RA will contact a participant a week prior to the due date and make an appointment. After 3 attempts to reach a participant by

phone, blinded RA will provide a daytime unannounced home visit. Participants will be informed of potential unannounced home visits during study consent.

Standard Care + Breastfeeding Incentives (SC+BFI). Participants in *SC+BFI* will receive all WIC usual care elements the *SC* group receives, plus (the only element that is different between groups) an escalating amount of monthly financial incentives contingent on observed BF and that incentives will be delivered immediately upon verified BF at each month. This will isolate the component of contingent incentives on BF which is hypothesized to produce the largest effect on continued BF rates. Blinded RA will ask participants to demonstrate BF and provide individual support to praise efforts to continue BF and problem-solve BF issues.

Contingent incentive component: The incentive amount was \$20.00 at the end of the first month and increased by \$10.00 every month until the end of 6 months. The maximum potential earning is \$270.00. The initial incentive value of \$20 was determined in the pilot study based on inputs from WIC-receiving Puerto Rican mothers as the minimum amount of monthly incentives that would motivate them to breastfeed (not to substitute for compensation from work outside of home). An escalating schedule of monthly incentives was employed based on previous incentive-based interventions to encourage continuous abstinence from substance use. A participant who successfully demonstrates BF receives the incentive amount on a pre-paid credit card at the end of each month. If a participant misses an appointment or does not demonstrate BF, she will not receive the incentive. The rest of the procedure will be the same as for *SC*. We will also provide bonus incentives of \$50 to mothers who selected full BF food package from WIC at baseline, 3 months and 6 months postpartum. Selection of the WIC food package will be verified through WIC.

- 10.4 Assessment.** All participants in both groups will be asked to complete periodic assessments at 1-, 3-, 6-, 9-, and 12-month postpartum intervals either at home or by phone. Assessments at 1, 3, and 6-month postpartum will be conducted by phone one week prior to home visit appointments and those at 9 and 12-month postpartum will be conducted in person. An RA will call a participant and make an appointment a week prior to the scheduled assessment date. The pilot study had the 97% follow-up rate at 6-month postpartum with this approach. Research measures for each timepoint is shown below. When a participant stops BF, she will be asked to explain the psychosocial or medical reasons of stopping BF, such as return to work, workplace policy on pumping, and lack of social support. Appointment cards will be given to participants for future appointments.
- 10.5 Payments.** Participants in *SC+BFI* will receive dollar amount incentives on a pre-paid credit card for breastfeeding. This type of system functions just like a Master Card and allows remote reloading. This system has been feasibly and effectively used by clinical populations. Un-blinded Project Coordinator will credit a dollar amount remotely on a Master Card for each participant. Participants in *SC* will receive a lump sum payment in form of retail gift cards at the end of 6 months based on the number of completed home visitations. The lump sum will be calculated after 6th month home visitation, and unblinded staff will notify the participant that the payment is ready for pick-up at the Temple University College of Public Health. All participants will receive retail gift cards for completing periodic assessments. Gift cards will be delivered in person on the day of in-person assessments, and at the next home visitation for phone-based assessments that are completed prior to the upcoming home visitation appointment. All participants will receive a gift basket at the 12-month visit as well.
- 10.6** Data source includes validated instruments for interview questions, breastfeeding observation records, and biological data and samples.

10.7 Description of data to be collected at each timepoint.

Screening/First home visitation:

Questionnaires to complete with staff between now and at the first home-based research assessment include:

Questionnaires	Description	When administered
Locator form	Participant contact information and emergency contacts	At the hospital floor
Sleep environment questionnaire	Sleep environment at home	At the hospital floor
Consent quiz	Questions based on the consent form	At home-based research assessment
Demographic questionnaire	Race/ethnicity, education, employment, pregnancy related questions	At home-based research assessment
LATCH	Breastfeeding observation checklist	At home-based research assessment
Iowa infant feeding attitude scale	General attitude for breastfeeding	At home-based research assessment
Breastfeeding self-efficacy scale	How confident and knowledgeable you are in breastfeeding	At home-based research assessment
Breastfeeding history/attitude	Own and family history of breastfeeding	At home-based research assessment
Acculturation scale	How comfortable you are with the American culture	At home-based research assessment
Brief infant sleep questionnaire	Infant sleep pattern	At home-based research assessment
Breastfeeding barriers	Identified barriers to continue breastfeeding and solutions	At home-based research assessment
History of tobacco, alcohol, and other substance use (including AUDIT-C)	Tobacco, alcohol, and other substance use in lifetime and prior to and during pregnancy and beliefs about use	At home-based research assessment
Fagerstrom test	Nicotine dependence	At home-based research assessment
Smoking cessation self-efficacy	Confidence of not smoking or maintaining abstinence	At home-based research assessment
TWEAK	Risk of maternal drinking	At home-based research assessment
Body uneasiness test	Body image concern	At home-based research assessment

Barratt impulsivity scale	How impulsive you think you are	At home-based research assessment
Daily log for infant feeding	Calendar on feeding patterns	At home-based research assessment
Daily log for pumping	Calendar on pumping patterns	At home-based research assessment
Edinburgh postnatal depression scale	How depressed you feel	At home-based research assessment
Employment	Employment situation and maternity leave	At home-based research assessment
Maternal/infant health survey	Recent medical events for moms and infants	At home-based research assessment
Breastfeeding self-efficacy scale	How confident and knowledgeable you are in breastfeeding	At home-based research assessment
Breastfeeding motivation	How motivated to breastfeed for 6 and 12 months	At home-based research assessment
Breastfeeding support	Type of social support for breastfeeding	At home-based research assessment
Confusion hubbub and order scale	Household environment	At home-based research assessment
Home smoking rules and household structure	About smoking rules at home and number of smokers living with the participant	At home-based research assessment
Menstrual Cycle	Questions about the last period	At home-based research assessment
Brief infant sleep questionnaire	Infant sleep pattern	At home-based research assessment

At baseline assessment as the first home-based assessment,

- Breastfeeding observation (using LATCH measure): Identify BF behavior: Audible swallowing, regular suck/swallow/breathe pattern, or visible milk in the infant's mouth. For pumping, observed pumping combined with observed resulting milk being fed to the infant.
- Maternal weight measure: Measured with a portable Health-O-Meter Floor Scale. Maternal weight will be measured at each assessment.
- Maternal waist and hip measure: Measured with a flexible measurement tape and applied at the waist and hip levels.
- Infant weight measure: Measured with a portable Health-O-Meter Digital Infant Scale. Research staff will not touch the infant but arrange the scale to place the infant. Infant weight will be measured before and after each breastfeeding observation in case of breastfeeding mothers to also measure the breast milk in the stomach.

- Infant length measure: Measured with Hopkins Measure Mat at home. Research staff will not touch the infant but arrange the measurement to place the infant.
- Saliva sample from mothers: Saliva samples in 3 collection tubes by Norgen Biotek Corporation will be used to collect maternal saliva samples by research staff. Saliva samples will be collected by noninvasive means defined by OHRP Category 3 (i.e., “uncannulated saliva collected either in an unstimulated fashion or stimulated by chewing gumbase or was or by applying a dilute citric solution to the tongue”). The saliva samples will be used for examining inflammatory and immunologic responses, hormones related to pregnancy, postpartum, and stress, and cotinine as nicotine metabolites and will not be used for genetic testing.
- Anal swab from infants: Swabs from Zymo Research Corporation will be used to take a rectal swab from infants by research staff. Anal swabs will not go beyond the rectum area for sampling. The specific method will follow the noninvasive method of anal swab sampling defined by WHO (i.e., “Insert the swab tip just past the anal sphincter and rotate gently. Withdraw the swab and examine to ensure that the cotton tip is stained with faeces. Place the swab in a sterile tube/container containing the appropriate transport medium.”).²⁸ The anal swab will be used for examining microbiome composition and will not be used for genetic testing.

Monthly home visitations:

Interview questions include:

Questionnaires	Description
Daily log for pumping	Calendar on pumping patterns
Daily log for infant feeding	Calendar on feeding patterns
Daily log for moms eating	Calendar on moms’ eating pattern
Barriers against breastfeeding	Barriers to problem solve to continue breastfeeding
Maternal/infant health survey	Recent medical events for moms and infants
Tobacco, alcohol, caffeine, marijuana use past 7-day	Recent use of licit substances
Household structure	Total number of smokers living with the participant
Menstrual cycle	Questions about the last menstrual period

- Breastfeeding observation (LATCH): Identify BF behavior: Audible swallowing, regular suck/swallow/breathe pattern, or visible milk in the infant's mouth. For pumping, observed pumping combined with observed resulting milk being fed to the infant.
- Maternal weight measure: Measured with a portable Health-O-Meter Floor Scale. Maternal weight will be measured at each assessment.
- Maternal waist and hip measure: Measured with a flexible measurement tape and applied at the waist and hip levels.
- Infant weight measure: Measured with a portable Health-O-Meter Digital Infant Scale. Research staff will not touch the infant but arrange the scale to place the infant. Infant

weight will be measured before and after each breastfeeding observation in case of breastfeeding mothers to also measure the breast milk in the stomach.

- Infant length measure: Measured with Hopkins Measure Mat at home. Research staff will not touch the infant but arrange the measurement to place the infant.
- Saliva sample from mothers: Saliva samples in 3 collection tubes by Norgen Biotek Corporation will be used to collect maternal saliva samples by research staff.

Periodic assessments:

All participants will be asked to engage in either phone-based or in-person periodic assessments. Assessments at 1-, 3-, and 6-month are phone assessment, and will be scheduled one week prior to monthly home visitation appointments. Assessments at 9- and 12-month are in-person at home. Interview questions include:

Questionnaires	Description	When administered
Breastfeeding motivation	How motivated to breastfeed for 6 and 12 months	Each assessment
Breastfeeding self-efficacy scale	How confident and knowledgeable you are in breastfeeding	Each assessment
Breastfeeding support	Type of social support for breastfeeding	Each assessment
Household structure	Total number of smokers living with the participant	Each assessment
Edinburgh postnatal depression scale	How depressed you feel	Each assessment
Sleep environment questionnaire	Sleep environment at home	1-month
Smoking cessation self-efficacy	Confidence of not smoking or maintaining abstinence	6-month
Brief infant sleep questionnaire	Infant sleep pattern	3-, 6-, 9-, and 12-month
Pittsburgh sleep quality index	How your sleep pattern is	3-, 6-, 9-, and 12-month
Barratt impulsivity scale	How impulsive you think you are	6- and 12-month
Daily log for pumping	Calendar on pumping patterns	9-, 12-month
Daily log for infant feeding	Calendar on feeding patterns	9-, 12-month
Breastfeeding barriers	Identified barriers to continue breastfeeding and solutions	9-, 12-month
Tobacco, alcohol, caffeine, marijuana use past 7-day	Recent use of licit substances	9-, 12-month
Menstrual cycle	Questions about the last menstrual period	9-, 12-month

Maternal/infant health survey	Recent medical events for moms and infants	9-, 12-month
Social constraints scale	People’s perception on social support	12-month
AUDIT-C	Recent alcohol use	12-month
TWEAK	Risk of maternal drinking	12-month
Participant satisfaction survey	How satisfied you are with the intervention	12-month
Holmes-Rahe life stress inventory	Stressful events that occurred in the last 12mos	12-month
Body uneasiness test	Body image concern	12-month
Employment	Employment situation and maternity leave	12-month
Infant behavior questionnaire	Behavior patterns and signs of your infant	12-month

- Breastfeeding observation (LATCH): Identify BF behavior: Audible swallowing, regular suck/swallow/breathe pattern, or visible milk in the infant's mouth. For pumping, observed pumping combined with observed resulting milk being fed to the infant at every in-person assessment.
- Maternal weight measure: Measured with a portable Health-O-Meter Floor Scale. Maternal weight will be measured at each assessment at every in-person assessment.
- Maternal waist and hip measure: Measured with a flexible measurement tape and applied at the waist and hip levels.
- Infant weight measure: Measured with a portable Health-O-Meter Digital Infant Scale. Research staff will not touch the infant but arrange the scale to place the infant. Infant weight will be measured before and after each breastfeeding observation in case of breastfeeding mothers to also measure the breast milk in the stomach.
- Infant length measure: Measured with Hopkins Measure Mat at home. Research staff will not touch the infant but arrange the measurement to place the infant.
- Anal swab from infants: Swabs from Zymo Research Corporation will be used to take a rectal swab from infants by research staff at 6- and 12-month. For 6-month, home-visiting staff will collect the anal swab at their 6-month home visitation.
- Saliva sample from mothers: Saliva samples in 3 collection tubes by Norgen Biotek Corporation will be used to collect maternal saliva samples by research staff at 9 and 12-month.

11.0 Risks to Participants:

- 11.1 Anticipated potential risks for participants who are enrolled in this study are 1) participants may be exposed to psychological by clinical and research staff and others; 2) participants may feel hesitance or concern completing research measures including breastfeeding observation; and 3) participants may be at risk of harm resulting from breach of confidentiality. They are considered minimal because they are not greater than those ordinarily encountered in daily life.

1. Participants may be exposed to psychological or physical coercion by clinical and research staff and others.

Protections: If research staff detects such psychological and physical coercion through direct and indirect observations during the study period, they will remind mothers that it is their choice to be in the study and that research staff will not tell anybody about the status of study participation. If a participant reports any psychological concern or shows 13 or greater score or endorsement in suicidal ideation in the Edinburgh postnatal depression scale, then staff will refer the participant to nearby community or hospital-based mental health treatment programs.

2. Participants may feel hesitance or concern completing research measures including breastfeeding observation.

Protections: Participants will be informed of potential hesitance or concern from completing research measures before signing the consent form and will be allowed to refuse to answer any question, provide biological samples, or let research staff observe BF or pumping without penalty. All research staff will be females. In the event of refusing to let research staff observe BF or pumping, mothers will not be eligible for receiving monthly financial incentives contingent on observed BF; however, they receive compensations for monthly nutritional monitoring and periodic assessments as those in the control condition. Their data will not be used for analyses. Direct observation of BF in a home setting has been acceptable to pilot study participants, and no participants refused to demonstrate BF in front of research staff that they built rapport with. Research staff will be trained in how to address hesitance or concern among participants and how to ask observing BF or pumping in a non-invasive manner.

3. Harm resulting from a breach of confidentiality: Breach of confidentiality could include unauthorized persons accessing information contained in their study files.

Protections: Every effort will be made to protect confidentiality of the information that participants provide. We will adhere to all applicable state and federal confidentiality regulations. All participants will be informed of all anticipated risks prior to giving their informed consent to participate in the research study. They will be told that they can discontinue participation at any time without penalty. Research materials will be encoded with a research number and will contain no other identifying information in order to protect participant confidentiality. The majority of the data associated with the study will be entered directly by research staff into a secured web-based data entry system (RedCap) via WiFi-connected laptop. Materials that need to be completed in paper-and-pencil format (only in case of equipment failure or lack of access to the internet) will be secured in locked filing cabinets in the research office located at Temple University College of Public Health and transported by research staff from the study site to Temple University College of Public Health in locked briefcases. Any information containing client identifiers will be kept in locked filing cabinets at Temple University College of Public Health or in a password-protected electronic file on a secure online database, separate from the data management security will be monitored by the Project Coordinator (PC) and the PI.

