- 3.1 We propose to examine the efficacy of monthly financial incentives contingent on observed breastfeeding (BF), supplemental to existing support from the Special Supplemental Nutrition Program for Women, Infants, and Children (WIC) program and home-based individual BF support, among low-income mothers. Low-income racial/ethnic-minority women breastfeed for an average duration of four months despite evidence-based recommendations by the American Academy of Pediatrics to exclusively breastfeed for six months of life in addition to continued breastfeeding through the first year. Insufficient duration of any BF is related to multiple maternal and child health problems, and increases in BF duration could be cost saving medically and societally. Though peer support has been effective in prolonging BF duration, the effect has not been as strong for WIC-eligible, low-income mothers. An incentive-based intervention was tested among low-income Puerto Rican mothers in a pilot study (R03HD077057) resulting in promising outcomes of monthly financial incentives contingent on observed BF for 6 months combined with WIC BF usual care, compared to WIC BF usual care only (BF rates: 89% vs. 44% at 1-month; $p = 0.01$; 89% vs. 17% at 3-month; $p < 0.01$; 72% vs. 0% at 6-month; $p < 0.01$; $N = 36$). We propose a 2-group parallel randomized controlled trial in which half of the 168 WIC-eligible mothers recruited to the trial will be allocated into each of the two study groups: (1) Standard Care BF Support (**WIC support + home-based individual support; Standard Care (SC)**) and (2) Incentives contingent on demonstrating successful BF (**SC + Breastfeeding Incentives; SC+BFI**). Participants randomized into SC will receive standard breastfeeding services from WIC and home visitations for individual support and problem-solving. Participants randomized into SC+BFI will receive the same services as Control except that monthly financial incentives are contingent on observed BF and delivered at the end of each month. The study will be conducted in two regional sites with high concentrations of low-income racial/ethnic minority mothers, Philadelphia, PA and Newark, DE. The primary outcome will be the BF rate for 6-month postpartum, the exploratory outcome will be the BF rate at 12-month postpartum, and the secondary outcomes will be infant outcomes (i.e., weight gain and emergency room visits). We hypothesize that SC+BFI will increase the BF rate by 25% at 6-month postpartum and have significantly lower infant weight gain and incidents of ER visits for infants at 3-month postpartum, compared to SC. We will track the costs of intervention, formula purchased by mothers, and infant medical care in both groups. We will also conduct interviews with corporate representatives and insurance companies to explore community- and policy-level support to

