9.1 Recruitment Methods

Study brochures will be placed at prenatal clinics and WIC offices. Staff can also actively engage in community outreach such as community baby shower events at WIC offices and prenatal breastfeeding education classes to share materials to advertise the study. Mothers who plan on or who have initiated BF postpartum will be identified and contacted by the mother's doctor either in person or phone call to tell them about the study. If interested, they will then be referred to a Research Assistant (RA) for invitation to the study.

Eligibility screening will be conducted during the hospital stay. The participants will be assured that all study data will be kept strictly confidential and will not affect the status of their treatment or services at the hospital or community service. Eligible mothers will be provided with the informed consent and HIPAA forms for mothers and babies. The RA will discuss the content of the study to ensure understanding of procedures, risks and benefits, human subject protections, and participants' autonomy. Mothers reporting current suicidal thoughts or attempts will be referred for psychosocial care at the hospital or in the community.

If the mother is not interested in participating in the study, staff will say "that's okay, we understand that all happening to you right now can be overwhelming. Thank you very much for your time! Congratulations again and let me know if you need any immediate assistance from the staff." If there is need for immediate breastfeeding and other support, staff will refer the mother immediately to the postpartum floor staff or a lactation consultant.

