9.3 Consent Process

The consent process will take place following the eligibility screening during the hospital stay. RAs will be involved in obtaining the written consent. The RA will discuss the content of the study to ensure understanding of procedures, risks and

benefits, human subject protections, and participants' autonomy to ensure the voluntary nature of study participation and human subject protection. RA will summarize the consent form paragraph by paragraph and ask questions at the end to ensure participants' understanding of the consent form. Women who would not be able to communicate with RA and understand the content of consent form will not be eligible for the study.

Infants: An infant of the parent will be included in the study: trained RAs will collect length and weight measurements of the child, and collect anal swabs for microbiome analysis. The permission of one parent is sufficient even if both parents are alive, known, competent, reasonably available, and shares legal responsibility for the care and custody of the child. Assent of the child will not be obtained because their capability is so limited that they cannot reasonably be consulted.

Two copies of consent signed by the study participant and RA will be obtained in person at the hospital – one for study staff and one for mom to keep for her records.

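### One fixed block size of 6, printed in the protocol, and no rule on who may see past assignments leave the next allocation open to prediction by a recruiter who can see them

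*Combined protocol and SAP*

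**What the plan says.** Section 10.2 specifies two arms and a single block size: "We will use a permuted block random assignment (with block size = 6". Section 3.1 gives equal allocation of 168 mothers: "half of the 168 WIC-eligible mothers recruited to the trial will be allocated into each of the two study groups".

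The sequence itself is protected. One co-investigator generates it and "keeps the original sequence in a password-protected electronic file that no other research staff can access"; RedCap is programmed to "automatically assign each participant to either condition". Section 10.2 then gives its reason for calling the allocation concealed: "Other research staff can only view the result of randomization so that the allocation process remains concealed". It does not say which staff roles this covers.

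The same section adds a second device, "We will use propensity score matching to randomize the participants based on study site, as well as Black race and Puerto Rican ethnicity", without saying how it combines with the blocks or within which lists the blocks run.

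On recruitment, section 9.1 says of interested mothers that "they will then be referred to a Research Assistant (RA) for invitation to the study", and section 9.3 says "RAs will be involved in obtaining the written consent". Section 22.1 requires research staff to know the protocol well, and the protocol prints the block size. Section 10.3 calls the RA who makes home visits blinded, and sections 10.5 and 14.2 name a separate unblinded Project Coordinator. No section reconciles these role descriptions with the sentence in 10.2 about who views results.

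**The concern.** Hiding the list protects against someone reading ahead. It does not protect against someone working out the next entry from the entries already used. With one known block size, once three mothers in a block have gone to one arm, the rest of the block must go to the other. Seeing only results is enough for that deduction, so the reason given in 10.2 does not support its conclusion.

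A recruiter who expects the incentive arm next could, without intending to, encourage a referred mother more or less according to how committed to BF she seems. That would make the arms differ at entry in a way that bears on the 6-month primary outcome, and covariate adjustment may not fully remove it. This is separate from whether BF is later observed blind.

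**Working it through.** The plan gives no figure for predictability, so there is none to reproduce.

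**Inputs.** Block size 6 with two arms (10.2); equal allocation and N = 168 (3.1). Hence 3 + 3 per block and 168 / 6 = 28 blocks on one list. The observer is assumed to know the block size and every earlier assignment on that list.

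**Allocations known for certain.** Of the C(6,3) = 20 equally likely orderings:

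- 4th place known if the first three match: 2/20 = 0.1
- 5th place known if the first four split 3–1: 8/20 = 0.4
- 6th place always known: 1.0

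The sum is 0.1 + 0.4 + 1.0 = 1.5 per block, or 1.5 / 6 = 25%. Over 28 blocks this is 28 × 1.5 = 42 of 168. The general formula for blocks of size 2m, 1/(m + 1), gives 1/4 at m = 3.

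**Best-guess success.** Guess the arm with more places left and toss a coin on ties. By place, the chance of being right is 0.5, 0.6, 0.6, 0.7, 0.7 and 1.0. The sum is 4.1, and 4.1 / 6 = 68.3%, against 50% for an unpredictable list.

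**If blocks run within strata.** This is an assumption, because 10.2 leaves the lists undefined. Incomplete last blocks lower the certain share slightly. Simulation gives about 24.3% (41 of 168) for two equal sites, and about 22% to 23% (38 to 39 of 168) for six to eight strata of assumed sizes. The observer must then also track each mother's stratum.

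**Bias.** Let g be the guess rate, and let d be the difference in expected 6-month BF between mothers recruited when the incentive arm is predicted and when Standard Care is predicted. A share g of the incentive arm and 1 − g of the Standard Care arm were recruited under an incentive-arm prediction. The bias is therefore

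(2g − 1)d = (2 × 0.683 − 1)d = 0.37d

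The documents give no value for d. For assumed values of 5 and 10 points, the bias is 1.8 and 3.7 points. The plan's hypothesised effect is 25%.

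**Effect of varied blocks.** With sizes 4, 6 and 8 drawn at random, and an observer who knows the set of sizes and all past results but not the size drawn, simulation gives about 2% certain (about 4 of 168). The guess rate stays at about 68%, so by the formula above the bias stays near (2 × 0.68 − 1)d = 0.36d. Varied blocks nearly remove certainty but not informed guessing. Only restricting sight of past results removes both.

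**The case against.** The strongest objection is that the key premise is inferred. A reader might conclude that recruiters do see the running assignments and that concealment has failed. The documents do not say so. Section 10.2 names no role and describes no running list. Section 10.3 describes blinded RAs, and 10.5 and 14.2 place payment knowledge with an unblinded coordinator. If the recruiting RAs are blinded in that sense, they can predict nothing. This stands, and it limits the point to an unsecured safeguard. It does not remove the point: no section says whether recruiting and home-visit RAs are the same people, and none bars recruiting RAs from viewing results.

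The 25% and 68% are upper figures for someone who tracks everything on one list. That also stands.

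The route to bias is narrow. Sections 6.1 and 9.1 have hospital staff or the mother's doctor identify and refer mothers, so RAs do not choose whom to approach first. Screening and consent take place during the hospital stay, so holding a mother back for a later slot would be hard. What remains is how strongly a referred mother is encouraged. The pilot in 5.3 shows some room for this: 13 of 61 women screened expressed interest but did not complete enrolment.

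Finally, varied block sizes alone barely change the guess rate. This is correct, and it is why restricting access carries equal weight in the fix.

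**Conclusion.** The point holds in limited form. The fixed, stated block size and the undefined access to results mean that unpredictability of the next allocation is not secured. The exposure ranges from none, for a recruiter who sees no assignments, up to 25% certain (42 of 168) and about 68% guessable for one who sees them all on a single list. If blocks run within strata, the certain count is about 38 to 41. The bias of about 0.37d further assumes that a recruiter acts on every guess, and d is an assumed quantity.

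The documents do not support saying that concealment does not hold: the sequence is centrally held and assignment is automatic. Nor do they show that any recruiter has used, or could in practice use, past results. This is a cheap improvement to the design.

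**What to change.** Make both changes together in section 10.2.

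1. **Access.** Set RedCap roles so that RAs who invite and consent mothers cannot view earlier assignments, and send each assignment to the already unblinded Project Coordinator. Name the roles that may see results, and reconcile this with the blinded RA of 10.3.
2. **Block sizes.** For remaining enrolment, replace the fixed block of 6 with randomly varied sizes (for example 4, 6 and 8), known only to the co-investigator who holds the list and left out of the staff version of the protocol. State in 10.2 which site or ethnicity lists the blocks run within.

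The cost is a new computer-generated list and a permission setting, with no extra staff. The drawback is that the largest possible imbalance per list rises from 3 (half of 6) to 4 (half of 8).
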